12.2 Endpoints

12.2.1 Definition of Primary Endpoint

PFS is defined as the time from Day 1 of treatment until the criteria for disease progression is met as defined by RECIST 1.1, MDA criteria or death as a result of any cause.

12.2.2 Definition of Secondary Endpoints

- Toxicities will be defined by the NCI Common Terminology Criteria for Adverse Events (NCI CTCAE) v5.
- Objective response rate (CR+PR) will be assessed via RECIST 1.1 or MDA criteria.
- Disease Control Rate (CR+PR+SD > 8 weeks) will be assessed via RECIST 1.1 or MDA criteria.
- Overall survival will be defined as the time from Day 1 of treatment until death from any cause.

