OBJECTIVES	 Primary Objective: Determine Progression Free Survival (PFS) of the combination of Guadecitabine and platinum in patients with extensive stage small cell lung cancer previously treated with platinum containing chemotherapy. Secondary Objectives: Evaluate the toxicity profile of the combination of Guadecitabine and carboplatin in patients with extensive stage small cell lung cancer patients previously treated with platinum containing chemotherapy. Estimate Objective Response Rate (ORR), Disease Control Rate (DCR, defined as Complete Response + Partial Response + Stable Disease), and Overall Survival (OS) of the combination of Guadecitabine and carboplatin in the above mentioned population. Exploratory Objectives: Measure platinum induced DNA adducts in peripheral blood mononuclear cells (PBMCs) and tumor tissue on Cycle 1 Day 1 and Cycle 2 Day 5 prior to carboplatin treatment. Methylation status change in PBMCs and tumor biopsy for global DNA and selected genes in tumor tissue on Cycle 1 Day 1 and Cycle 2 Day 5 prior to carboplatin treatment. Analyze IHC expression of EZH2 and EZH2 target genes on Cycle 1 Day 1, Cycle 2 Day 5 prior to carboplatin treatment and at progression (optional). EZH2 expression changes will be correlated with response to Guadecitabine in combination with carboplatin. Determine circulating tumor cell (CTC) burden prior to initiating treatment.
STUDY DESIGN	Phase II, open-label, single arm, single-stage study. A total of 34 evaluable patients will be enrolled, of which we expect 70% to be chemotherapy sensitive and 30% to be chemotherapy resistant. This study is powered for chemotherapy sensitive patients. Chemotherapy resistant patients will be enrolled but analyzed separately and descriptively only.

KEY ELIGIBILITY CRITERIA (See Section 3 for full eligibility criteria)

Inclusion Criteria

- 1. Male or female subjects, age \geq 18 years.
- 2. Histological or cytological diagnosis of small cell lung cancer; extensive stage disease.
- 3. Patients must have received first line therapy with a platinumbased chemotherapy. Patients should not have received more than 1 prior line of chemotherapy (could have received immunotherapy which does not count as chemotherapy)
- 4. ECOG PS 0-1
- 5. Measurable disease as per RECIST v1.1. Subjects may have bone-only disease.
- 6. Adequate bone marrow, liver, and renal function, as assessed by the following laboratory requirements:
 - o Hemoglobin $\geq 9.0 \text{ g/dL}$

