2.2.2 Secondary Endpoints

- Occurrence of all treatment related toxicities as defined by the NCI Common Terminology Criteria for Adverse Events (NCI CTCAE) v5.0
- ORR will include confirmed complete response (CR) + confirmed partial response (PR) and will be determined as per RECIST 1.1 or MDA criteria.
- DCR defined as CR + PR + Stable Disease (SD) per RECIST 1.1 or MDA criteria
- OS as defined as the time from Day 1 of treatment until death from any cause

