9.8 Definitions for Response Evaluation – RECIST 1.1

9.8.1 Objective Response Rate

The objective response rate is the proportion of all subjects with confirmed PR or CR according to RECIST 1.1, from the start of treatment until disease progression/recurrence (taking as reference for progressive disease the smallest measurements recorded since the start of treatment).

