9.8.2 Disease Control Rate

The disease control rate is the proportion of all subjects with stable disease (SD) for 8 weeks, or partial response (PR), or complete response (CR) according to RECIST 1.1, from the start of treatment until disease progression/recurrence (taking as reference for progressive disease the smallest measurements recorded since the start of treatment).

Version Date: 18MAR2020 Confidential Page 25 of 41

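### Disease control rate is defined both with and without an 8-week minimum for stable disease, and the first planned scan falls on that cut-off

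*Combined protocol and SAP*

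**What the plan says.** DCR is defined in four places:

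- Synopsis, Objectives: "Disease Control Rate (DCR, defined as Complete Response + Partial Response + Stable Disease", with no minimum duration.
- Section 2.2.2: "DCR defined as CR + PR + Stable Disease (SD) per RECIST 1.1 or MDA criteria", again with no minimum.
- Section 9.8.2: "The disease control rate is the proportion of all subjects with stable disease (SD) for 8 weeks", or PR or CR, followed by the span "from the start of treatment until disease progression/recurrence".
- Section 12.2.2: "Disease Control Rate (CR+PR+SD > 8 weeks) will be assessed via RECIST 1.1 or MDA criteria".

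The SD definition in Section 9.5 and the best-response table in Section 9.7 set no minimum duration.

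For ORR, Section 2.2.2 says "ORR will include confirmed complete response (CR) + confirmed partial response (PR") and Section 9.8.1 says "The objective response rate is the proportion of all subjects with confirmed PR or CR according to RECIST 1.1". Section 12.2.2 gives only "Objective response rate (CR+PR) will be assessed via RECIST 1.1 or MDA criteria". No section says whether a CR or PR counted in DCR must be confirmed.

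Sections 9.8.1 and 9.8.2 take all subjects as the denominator. Section 12.6.2 estimates both rates, with 95% confidence intervals, in the efficacy evaluable population. Section 12.5 limits that set to treated subjects who had a post-baseline assessment or died before one.

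The study calendar and its footnote 4 place the first on-treatment scan before Cycle 3 Day 1 and the next at the safety visit, 30 days (± 7) after the last dose.

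**The concern.** Two analysts could each follow the document and report different DCRs from the same data. The disagreement is over whether a minimum applies at all. Where it does apply, Section 12.2.2 gives neither a start nor an end for the 8 weeks, and the span in Section 9.8.2 can be read in two ways.

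This matters because the 8-week mark coincides with the nominal date of the first scan. If SD is timed to the last scan that shows it, a patient with SD at that scan and progression at the next may count or not according to the day of the visit. Section 13.4 requires results for all secondary objectives to be posted, so the figure will be public, and the definition should not be chosen after the data are seen.

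A smaller point is the denominator. Leaving out living treated patients who have no post-baseline assessment can only raise ORR and DCR, because such patients cannot be in either numerator.

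**Working it through.** **The plan's own figure.** No figure is given for DCR or ORR. The only computed design figure is n = 24 for PFS (Section 12.3: one-sided 0.10, 80% power, median 3 versus 6 months). With a sign test at 3 months and exponential PFS, p0 = 0.50 and p1 = 0.5^(3/6) = 0.7071. Then n = [(1.2816 × 0.5 + 0.8416 × √(0.7071 × 0.2929)) / 0.2071]² = 24.4, and power at n = 24 is 79.4%. The figure reproduces, and it does not involve DCR.

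**Calendar.** Inputs are 28-day cycles (Schema), a ± 3-day window on Day 1 and Day 5 visits (Section 5.1), delays of up to 2 weeks (Section 6.1), and the scan times in Section 7. Days are elapsed from Cycle 1 Day 1.

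- Cycle 3 Day 1: 2 × 28 = 56 days, exactly 8.0 weeks.
- With the visit window: 53 to 59 days. No limit is given on how far ahead of the visit the scan may be done.
- With one or two cycles each delayed by 14 days: 56 + 14 = 70, or 56 + 28 = 84 days.
- Cycle 4 Day 5: 3 × 28 + 4 = 88 days. Safety scan: 88 + 30 = 118 days (111 to 125), or 16.9 weeks.

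**Classification of a patient with SD at the first scan and progression at the next.**

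- Any SD: counts.
- SD ends at progression: about 118 days, so the patient counts with or without the minimum.
- SD ends at the last SD scan, more than 8 weeks required: a scan on days 53 to 56 fails and on days 57 to 59 passes.
- SD ends at the last SD scan, at least 8 weeks required: days 53 to 55 fail and days 56 to 59 pass.
- SD ends at the last SD scan, first scan moved to day 70 or 84 by a delayed cycle: passes either way.

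**Size under the last-SD-scan reading.** Assume exponential PFS, S(d) = 0.5^(d / 30.44 / median), on-time cycles, and scans at days 56 and 118.

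- Median 3 months: S(56) = 0.654 and S(118) = 0.408. The difference is 24.5 points; 24 × 0.245 = 5.9 patients.
- Median 6 months: S(56) = 0.809 and S(118) = 0.639. The difference is 17.0 points; 24 × 0.170 = 4.1 patients.

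These are upper bounds for this group. They are reached only if everyone who progresses or dies between the two scans had SD at the first, or an unconfirmed response treated as SD. Patients with SD at the first scan and no later scan are not in this calculation. One patient is 1/24 = 4.2 points in the sensitive group and 1/10 = 10 points in a resistant group of 10.

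**What such a shift looks like.** Moving four patients, for example from 12/24 to 16/24, takes DCR from 50.0% (exact 95% CI 29.1 to 70.9) to 66.7% (44.7 to 84.4).

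**Denominator.** As an assumed illustration, take 12 controlled patients among 24 treated, of whom two are alive without an assessment: 12/24 = 50.0% against 12/22 = 54.5%.

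**The case against.** The strongest reply is that Section 9.8.2 already supplies the duration rule. SD is the only component there with a time requirement, and the sentence goes on to name a span from treatment start to progression. Read that way, SD ends at progression and the effect is about zero. That reading is plausible, but the text does not fix it. Section 9.8.1 attaches the same words to ORR, where they can only be an observation window, and Section 12.2.2 omits them. Even on this reading, a patient with SD and no later scan, or who starts new treatment, has no stated end date.

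Several stronger readings are tempting and should not be drawn:

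- A reader might infer a third definition from the strict inequality in Section 12.2.2. Signs in this text are not reliable enough for that: Section 12.1 prints the same sign for both sensitivity groups, where Sections 1.1 and 4 give opposite ones.
- A reader might see a conflict in Section 9.8.2 naming RECIST 1.1 alone. Section 9.8 is the RECIST section, Section 9.9 is its counterpart for bone-only disease, and Section 12.5 assigns MDA criteria to those patients.
- A reader might infer that confirmation of response is in dispute. Sections 2.2.2 and 9.8.1 both require it for ORR, and Section 12.2.2 reads as shorthand. For DCR an unconfirmed response would normally fall to SD, so it matters only through the duration question.
- A reader might take the denominators as flatly contradictory. Section 12.6.2 is probably the operative rule, and all subjects can mean all subjects in that set. What stands is that the evaluable set drops living treated patients without an assessment.

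**Conclusion.** The conflict over DCR is explicit and unresolved: two places have no minimum for SD and two have an 8-week minimum. Its effect depends on a choice the plan leaves open. It is about zero if SD runs to progression. If SD ends at the last scan showing it, it is at most about 17 to 25 points (4 to 6 of 24 patients), given exponential PFS with a median of 6 or 3 months and on-time cycles. The documents do not support saying that visit timing must decide the result, only that it does under the second reading.

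The denominator point is minor, and its direction is always upward. A reader might infer that the trial's conclusion is at risk. It is not: ORR and DCR are secondary estimates without a test or decision rule, and the PFS test and n = 24 are unaffected. The wording should still be settled before analysis.

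**What to change.** Use one DCR definition in the synopsis and Sections 2.2.2, 9.8.2 and 12.2.2. It should state:

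- the minimum SD duration, if any, with its inequality;
- that the duration starts on Day 1 of treatment;
- whether it ends at the last scan showing SD or at progression;
- if it ends at the last SD scan, a classification tolerance chosen by the sponsor so that an on-schedule pre-Cycle 3 scan showing SD qualifies. A threshold of 49 days (56 − 7) is one example only: the ± 7 days in footnotes 4 and 10 is not clearly given to that scan;
- that an unconfirmed response counts as SD for DCR.

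Report ORR and DCR over all treated patients in each group, counting those without a post-baseline assessment as non-responders and not controlled. Align Sections 9.8.1, 9.8.2 and 12.6.2 with this.

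The cost is wording only, with no change to visits or scans. ORR and DCR may come out slightly lower, because unassessed patients count as failures.

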12.3 Sample Size and Accrual

For the chemo-sensitive group, when the sample size is 24, a non-parametric test (single-group) with a one-sided 0.10 significance level will have 80% power to detect the difference between a median survival of 3.0 months vs 6.0 months assuming an accrual period of approximately 12 months and maximum follow-up of 24 months (i.e. would allow for up to 12 months of follow-up after accrual ends). With 24 in the chemo-sensitive group, we expect to enroll approximate 34 subjects total, thus will have approximately 10 chemo-resistant patients to generate pilot data.

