 - o Absolute neutrophil count (ANC) ≥1,500/mm3
 - o Platelet count >100,000/mm3
 - Total bilirubin ≤1.5 x upper limit of normal (ULN). For subjects with Gilbert's Disease, Total bilirubin ≤3 x ULN
 - o ALT and AST ≤2.5 x ULN. For subjects with documented liver metastases, ALT and AST ≤5×ULN
 - Estimated glomerular filtration rate (eGFR) ≥ 60 mL/minute/1.73 m2 as determined using the (by Cockcroft-Gault formula)
- 7. Male and female subjects of child- bearing potential must agree to use contraception as outlined in Section 5.4 from the screening visit through 6 months after the last dose of study drug.

Exclusion Criteria

- 1. Platinum refractory disease defined as disease progression during platinum containing chemotherapy. Progression following platinum based treatment is not an exclusion.
- 2. Prior therapy with a hypomethylating agent.
- 3. Previously untreated (non-irradiated), symptomatic brain metastases. No prior treatment is required for non-symptomatic brain metastases. Previously treated symptomatic brain metastases are permitted.
- 4. Unstable or clinically significant concurrent medical condition, psychiatric illness or social situation that would, in the opinion of the investigator, jeopardize the safety of a subject and/or their compliance with the protocol.
- 5. Clinically significant acute infection requiring systemic antibacterial, antifungal, or antiviral therapy. (Suppressive therapy for chronic infections allowed, for example: Subjects with HIV/AIDS with adequate antiviral therapy to control viral

	load would be allowed. Subjects with viral hepatitis with controlled viral load would be allowed while on suppressive antiviral therapy.) 6. Hypersensitivity to (IMP) or components of the study treatment regimen. 7. Treated with any investigational drug within 3 weeks of first dose of study treatment.
STATISTICAL CONSIDERATIONS	Null Hypothesis: Median PFS with combination of Guadecitabine with carboplatin in patients with extensive stage small cell lung cancer previously treated with platinum containing chemotherapy is 3 months or less.
	Alternative Hypothesis: Median PFS with combination of Guadecitabine with carboplatin in patients with extensive stage small cell lung cancer previously treated with platinum containing chemotherapy is 6 months or longer.
	Acceptable Type I (alpha) error: 10% (one sided) Acceptable Type II (beta) error: 20% Power: 80%

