	This study is powered for chemotherapy sensitive patients. Chemotherapy resistant patients will be enrolled but analyzed separately and descriptively only. For the chemosensitive group, when the sample size is 24, a non-parametric test (single-group) with a one-sided 0.10 significance level will have 80% power to detect the difference between a median survival of 3.0 months vs 6.0 months. With 24 patients in the chemo-sensitive group, we expect to enroll approximate 34 subjects total, thus we will have approximately 10 chemo-resistant patients to generate pilot data from.
TOTAL NUMBER OF SUBJECTS	N = 34
ESTIMATED ENROLLMENT PERIOD	Estimated 18 months
ESTIMATED STUDY DURATION	Estimated 12 months

TABLE OF CONTENTS

Sch	ema	7
1.	Background and Rationale	8
2.	Study Objectives and Endpoints	
3.	Eligibility Criteria	
4.	Subject Registration	
5.	Treatment Plan	
6.	Toxicities and Dose Delays/Dose Modifications	
7.	Study Calendar & Evaluations	
8.	Biospecimen Studies and Procedures	
9.	Criteria for Disease Evaluation	
10	Drug Information	
11	Adverse Events	
12	Statistical Methods	
13	Trial Management	
14.	Data Handling and Record Keeping	
15	Ethics	
16	References	
- 0	110101 011000	••••••••••••

SCHEMA

- ES SCLC patients
- Must have prior treatment with platinum containing chemotherapy regimen
- PS 0-1
- Adequate organ function

Treatment Regimen

Guadecitabine 30mg/m² subcutaneously Days 1-5 Carboplatin AUC of 4 intravenously on Day 5 Continue for 4 cycles; 1 Cycle = 28 Days

Disease Assessment after completion of 4 cycles of treatment Continue follow up per protocol

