- 4: Tumor response assessment will consist of evaluation by CT or PET CT scan of chest. An MRI, CT or PET CT scan of the abdomen and pelvis may be done if there is measurable disease that is not detectable by CT or PET CT of the chest. A bone scan may be used for subjects with bone only disease or if there is suspicion of bone metastasis. Imaging will be performed at screening, prior to Cycle 3 and at the D30 safety follow up visit (± 7 days). Imaging selected for each subject should remain the same throughout the study. If tumor assessments are available for subjects who have not yet experienced progressive disease (PD) at the time treatment is discontinued, the follow-up tumor evaluations will be documented in the eCRF until PD or death is confirmed, or until another treatment is initiated.
- 5: Archival tissue is required if available and should be identified at screening and shipped by C2D1. If archival tissue is not available, subjects may still be eligible. Biopsies will be obtained prior to C1D1 from 15 patients with easily accessible disease regardless of availability of archival tissue. These same 15 patients will be required to undergo a repeat biopsy prior to treatment on C2D5 if clinically feasible. These same subjects will have the option to undergo a biopsy at progression/safety visit. See Correlative Laboratory Manual (CLM) for detailed instructions.
- 6: Whole blood will be collected for somatic baseline and CTCs prior to treatment C1D1. Whole blood will be collected prior to treatment C1D1, C2D5 and at progression/Safety Follow Up visit for isolation of peripheral blood mononuclear cells. See CLM for detailed instructions.
- 7: Samples for banking for future unspecified cancer related research include: Whole blood: collected prior to treatment on Cycle 1 Day 1. Whole blood for Serum and Plasma: collected prior to treatment on Cycle 1 Day 1 and at the 30-day Safety Follow-up visit. See CLM for detailed instructions.

Version Date: 18MAR2020 Confidential Page 20 of 41

- 8: CBC and CMP to be performed during screening for eligibility and on C1D1 prior to treatment. For the remainder of the Cycles, CBC and CMP may be performed within 4 days prior to Day 1 of treatment.

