- 9: The safety follow-up visit should only occur when subjects permanently stop study treatment for whatever reasons (toxicity, progression, or at discretion of site investigator) and should be performed 30 days (± 7 days) after the last dose of treatment. Subjects who have an ongoing Grade ≥ 2 or serious AE (SAE) at this visit will continue to be followed until the AE resolves to ≤ Grade 1 or baseline, deemed clinically insignificant, and/or until a new anti-cancer treatment starts, whichever is earlier.
- 10: Long-term follow up will occur in all subjects until documented disease progression. Radiology imaging should be performed every 2 months (± 7 days). Subjects who discontinue treatment for any reason without documented disease progression will be followed every 2 months for 1 year (± 14 days). Once disease progression is documented, subjects will enter a survival follow up period every 3 months for 1 year from the time of documented progression. Follow up may be accomplished via clinic visit, phone call, or other avenues as appropriate.

Version Date: 18MAR2020 Confidential Page 21 of 41

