9.8.3 Progression Free Survival

A measurement from Day 1 of treatment until the criteria for disease progression is met as defined by RECIST 1.1 or death, whichever occurs first. Subjects who have not progressed will be right-censored at the date of the last disease evaluation.

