12.6 Data Analysis Plans

12.6.1 Analysis Plans for Primary Objective

In the efficacy evaluable population, in the chemo-sensitive group only the primary endpoint of PFS will be separately compared to the historical control rate of 3 months using a one-sided Sign Test for censored data (35). In both the chemo-sensitive and -resistant groups, PFS overall will be estimated with a Kaplan-Meier curve and median PFS with a 95% confidence interval.

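### The 80% power stated for 24 chemo-sensitive patients is not what the named sign test attains: about 75% power at 7.6% size, under assumptions the plan leaves unstated

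*Combined protocol and SAP*

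**What the plan says.** Section 12.3 states that "when the sample size is 24, a non-parametric test (single-group) with a one-sided 0.10 significance level will have 80% power" for a median of 3.0 versus 6.0 months, with about 12 months of accrual and up to 24 months of follow-up. The Synopsis (Statistical Considerations) repeats the claim. It also lists "Acceptable Type II (beta) error: 20" per cent, with a one-sided type I error of 10% and power of 80%.

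Section 12.6.1 names the test: PFS in the chemo-sensitive group is "compared to the historical control rate of 3 months using a one-sided Sign Test for censored data".

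Three passages bear on whether status at 3 months is known:
- Section 9.8.3: "Subjects who have not progressed will be right-censored at the date of the last disease evaluation".
- Section 7, footnote 4: "Imaging will be performed at screening, prior to Cycle 3 and at the D30 safety follow up visit".
- Section 7, footnote 9: the safety visit falls 30 days (± 7) "after the last dose of treatment".

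The documents give no PFS distribution, dropout rate, rejection cut-off or attained size. They do not give the variance or scale of the test, and they do not say whether the 80% is exact or approximate.

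**The concern.** A sign test against a 3-month median turns on how many patients are progression-free at 3 months. With 24 patients that count moves in whole steps, so the attained size and power can differ noticeably from a smooth large-sample figure. Section 12.3 gives one power figure and no cut-off, so a reader cannot tell which kind it is.

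This is the trial's only powered comparison; the chemo-resistant group is described only. If the attained type II error is nearer 25% than 20%, a negative result carries less weight than the plan implies. The attained size matters as well, because it is not 10% and its direction depends on assumptions that the plan does not state.

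**Working it through.** **Inputs.** From section 12.3 and the Synopsis: n = 24, one-sided alpha 0.10 (critical z = 1.2816), medians 3.0 and 6.0 months. From section 12.6.1: sign test against 3 months. The stated accrual and follow-up leave at least 12 months of potential follow-up per patient, so there is no administrative censoring before month 3. *Assumed*, because the documents are silent: exponential PFS. Then S(3) = 0.50 under the null and 0.5^(3/6) = 0.7071 under the alternative.

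**1. Reproducing the 80%.** Normal approximation with null variance in the critical value and alternative variance in the power:

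Φ{[√24 × (0.7071 − 0.5) − 1.2816 × 0.5] / √(0.7071 × 0.2929)} = Φ{(1.0146 − 0.6408) / 0.4551} = Φ(0.821) = 79.4%.

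**2. Where the named test rejects, with 3-month status known for all 24.** With no early censoring, the Kaplan-Meier estimate at 3 months is k/24.

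| k of 24 | S(3) | z, null variance 0.5²/24 | z, Greenwood variance | Reject? |
|---|---|---|---|---|
| 15 | 0.625 | 1.225 | 1.265 | No |
| 16 | 0.667 | 1.633 | 1.732 | Yes |

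**3. Attained size and power, exact binomial.**

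| Cut-off | Size, P(X ≥ k given 0.5) | Power, P(X ≥ k given 0.7071) |
|---|---|---|
| 16 | 7.6% | 75.1% |
| 15 | 15.4% | 86.5% |

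No fixed cut-off at n = 24 gives both size of at most 10% and power of at least 80% under these conditions.

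**4. Early censoring (assumed rates).** Simulation of the Kaplan-Meier/Greenwood test, exponential PFS, exponential dropout by month 3, 100,000 runs:

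| Dropout by month 3 | Size | Power |
|---|---|---|
| 0% | 7.6% | 75.1% |
| 5% | 9.0% | 77.1% |
| 10% | 10.1% | 77.8% |
| 15% | 10.7% | 77.8% |
| 20% | 11.0% | 77.3% |

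With the null variance instead (20,000 runs), 10% and 20% dropout give power 78.4% and 78.5% at size 10.1% and 11.8%. Censoring smooths the steps, but 80% is not reached.

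**5. PFS shape (assumed Weibull, same medians, complete status, cut-off 16).** S(3) = 0.5^(0.5^shape) under the alternative. Size is unchanged because S(3) = 0.5 under the null.

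| Shape | S(3) | Power |
|---|---|---|
| 0.8 | 0.672 | 61% |
| 0.9 | 0.690 | 69% |
| 1.1 | 0.724 | 81% |
| 1.2 | 0.740 | 85% |

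**6. Dating of progression.** The scan before Cycle 3 falls at about day 56. After four undelayed cycles, Cycle 4 Day 5 is day 3 × 28 + 5 = 89, so the safety visit is at about day 89 + 30 = 119. A patient who completes treatment has no scheduled scan near month 3. If a share q of the progressions between day 56 and month 3 is first dated after month 3, the apparent S(3) becomes S(3) + q[S(day 56) − S(3)]. With cut-off 16 and exponential PFS:

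| q (assumed) | Apparent S(3), null / alternative | Size | Power |
|---|---|---|---|
| 10% | 0.515 / 0.717 | 10.0% | 78.5% |
| 25% | 0.538 / 0.733 | 14.5% | 83.2% |
| 50% | 0.577 / 0.758 | 24.9% | 89.7% |

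The documents support no particular value of q, so these rows show sensitivity only.

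**The case against.** **The test form is not fully specified.** Section 12.6.1 gives neither scale nor variance. The margin at 15 of 24 is thin for Greenwood (1.265 against 1.2816), and on the log scale 15 of 24 gives z = 1.411 and rejects. That version would have 86.5% power, but at size 15.4%, so it is not a 10% test. Log-log (1.155) and arcsine (1.238) do not reject at 15. With 20% dropout, power and size are 72.5% and 8.6% on the log-log scale, and 80.6% and 13.3% on the log scale. This objection stands: the 75–78% range belongs to the untransformed form, and the form must be stated with it.

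**The assumptions could equally favour the sponsor.** A Weibull shape of 1.1 gives 81%. That is true, so 75% is a conditional figure and not an estimate of what the trial will attain. But section 12.3 offers no such shape in support of its 80%.

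**The scan gap is only partial.** A patient found progression-free at about day 119 was progression-free at month 3, and deaths are PFS events in their own right and do not depend on the scans. Only progressions between the scans, and dropouts in that gap, are affected. This also stands.

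**Readings the documents do not support.**
- That the 80% is an arithmetic slip: it reproduces to within a point by a standard approximation. That this approximation was the method used is itself an inference.
- That the type I error is inflated: with complete status it is 7.6%, below the limit. It exceeds 10% only under assumed dropout or late dating.
- That the 20% type II error in the Synopsis is wrong: it is a design tolerance, not an attained figure.
- That the accrual wording undermines power: "A total of 34 evaluable patients will be enrolled, of which we expect 70% to be chemotherapy sensitive" and "With 24 patients in the chemo-sensitive group, we expect to enroll approximate 34 subjects total" agree in expectation (34 × 0.70 = 23.8).

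**Conclusion.** The concern holds in conditional form. With exponential PFS, complete 3-month status and the untransformed sign test, 24 patients give 75.1% power at 7.6% one-sided size, with rejection from 16 of 24. Power is about 5 points below the stated 80%, and the type II error is about 25% against a 20% target. The cause is the discreteness of the test at n = 24. An assumed 5–20% early dropout narrows the gap (power about 77–78%, size about 9–11%) without closing it.

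Confidence is high in this arithmetic under the stated conditions. It is moderate for what the trial would actually attain, because PFS shape, early censoring and the dating of progression between scans are all unstated and each can move the figures by more than the 5-point gap or change the attained size.

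The consequence is modest for a single-arm phase II study, and neither the sample size nor the test has to change. The statement should still be corrected, because it describes the only powered comparison.

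**What to change.** In the Synopsis (Statistical Considerations) and section 12.3, replace the 80% with the attained figures for the named test: about 75% power at about 7.6% one-sided size, rejecting at 16 or more of 24 progression-free at 3 months, with complete 3-month status. Beside them, state:
- the variance and scale of the sign test (also in section 12.6.1);
- exponential PFS as the assumed distribution;
- the assumed censoring before month 3 and the resulting range (about 77–78% power and 9–11% size for 5–20% dropout, untransformed Greenwood form);
- that 3-month status is assumed known although no scan is scheduled near month 3, and that the figures do not hold if earlier progressions are dated only at the later scan.

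Keep n = 24 and the test. Leave the 20% type II error in the Synopsis as the design target, but change or annotate the 80% power line next to it to say that attained power is about 75% under these assumptions.

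As a separate minor matter, the sponsor should reconcile the accrual wording (34 evaluable patients in total, or 24 chemo-sensitive patients with about 34 expected) and say which count closes enrolment.

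The cost is wording only. The stated power becomes less favourable, and the plan openly shows an attained type II error above its own target; whether to accept that is the sponsor's decision.
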